CARTISTEM® PHASE I/IIa CLINICAL TRIAL PROTOCOL MP-0201-01

Version 3.2 Date: 15 March, 2017

CARTISTEM® PHASE I/IIa CLINICAL TRIAL PROTOCOL

CARTISTEM®

page 1 of 137

CONFIDENTIAL: These all contents herein are the sole property of MEDIPOST Co., Ltd. Any reproduction or distribution of this document without the written consent of MEDIPOST Co., Ltd is prohibited. Copyright © 2017 MEDIPOST Co., Ltd.

Name of Company Name of Product: Umbilical Cord Blo Ex vivo, Combined	Protocol #: MP-0201-01								
Protocol Title	Evaluation of Safety and Exploratory Efficacy of CARTISTEM [®] , a Cell Therapy Product for Articular Cartilage Defects: A Phase I/IIa Clinical Trial in Patients with Focal, Full-thickness Grade 3-4 Articular Cartilage Defects of the Knee								
Clinical Phase	Phase I/IIa								
Study Overview	dy Overview CARTISTEM [®] will be administered at doses ranging from 0.5×10 ⁷ to 2.25×10 ⁷ hUCB-MSC (0.25×10 ⁷ cells/cm ² ; 0.5 mL/cm ² with 0.5×10 ⁷ MSC/mL) to patients with focal, full-thickness, Grade 3-4 articular cartilage defects of ≥ 2cm ² in size. Safety: Patient safety will be assessed step-wise with increasing levels of total hUCB-MSC and HA exposure: a total of 12 patients will be enrolled and treated with CARTISTEM [®] to evaluate whether dose limiting toxicity (DLT) is detected. DLT is defined as toxicity or adverse event of Grade 3 or higher [80 points or higher for pain] in two or more events at the surgery site among swelling, tenderness, range of motion, and pain in any one visit. DLT is also defined as adverse drug reaction of Grade 3 or higher in the Common Toxicity Criteria Adverse Events (CTCAE), Version 4.0, with the exception of the following events and that they are unresolved for 7 consecutive days, despite medical interventions: ✓ Abnormal results in lab test (Acidosis, Hyponatremia, Hyperbilirubinemia, etc.) ✓ Abnormal results in lab test (Acidosis, Hyponatremia, Hyperbilirubinemia, etc.) ✓ Pain, defined as severe pain; limiting self-care ADL ✓ Pain, defined as severe pain; limiting self-care ADL								
	✓ Fever, defined as > 40.0 degrees C (> 104.0 d	degrees F) for > 24 hours							
	Initially, 6 patients with lesion sizes of 2-5 cm ² w (Dosage A); if dose limiting toxicity is not detect after administration, an additional 6 patients, with	ed during a 12 week period							

page 2 of 137

CONFIDENTIAL: These all contents herein are the sole property of MEDIPOST Co., Ltd. Any reproduction or distribution of this document without the written consent of MEDIPOST Co., Ltd is prohibited. Copyright © 2017 MEDIPOST Co., Ltd.

	_
	5 cm ² , will be enrolled and treated (Dosage B) to further evaluate safety.
	Efficacy: Efficacy will be evaluated with several validated clinical outcome instruments as primary endpoints as well as non-invasive structural assessment utilizing high-resolution magnetic resonance imaging with cartilage-specific sequences as a secondary endpoint.
Objectives:	
Primary Objective	To evaluate the safety of CARTISTEM [®] administration
Secondary Objectives	To evaluate the exploratory efficacy (improvement in Clinical Scores and regeneration of defective cartilage as assessed by Radiological images) of CARTISTEM [®] .
Diagnosis and Main Criteria for Inclusion	 Patients must meet the following criteria to be eligible for the study; Patients with an intended- to- treat single focal, full-thickness cartilage defect (ICRS [International Cartilage Repair Society] Grade 3 or 4) of the knee as a result of ageing, trauma, or degenerative diseases. Age ≥ 18 years old Size of the articular cartilage lesion is ≥ 2 cm² Swelling, tenderness and active range of motion ≤ Grade II Joint pain : 20-mm - 60-mm on VAS (Visual Analog Scale) at the time of Screening Appropriate blood coagulation, kidney and liver function laboratory parameters: ✓ PT(INR) < 1.5, APTT <1.5×control ✓ Creatinine ≤ 2.0 mg/dL, Albumin ≤ trace in urine dipstick test ✓ Bilirubin ≤ 2.0 mg/dL, AST/ALT ≤ 100 IU/L Ligament instability ≤ Grade II Lower extremity alignment within 5 degrees of the neutral weight bearing axis No meniscal surgery within the past 3 months and more than 5mm of meniscal rim remaining Ability and willingness to fully participate in the post-operative rehabilitation program Subject is informed of the investigational nature of this study, voluntarily agrees to participate in the study, and signs an IRB-approved informed consent prior to performing any of the screening procedures

[figure not shown]
page 3 of 137

CONFIDENTIAL: These all contents herein are the sole property of MEDIPOST Co., Ltd. Any reproduction or distribution of this document without the written consent of MEDIPOST Co., Ltd is prohibited. Copyright © 2017 MEDIPOST Co., Ltd.

	• Body Mass Index (BMI) $\leq 35 \text{ kg/m}^2$
Criteria for Exclusion	 Patients who have been treated previously and are asymptomatic Avascular necrosis/ osteonecrosis Autoimmune or inflammatory joint disease History of infection within the past 6 weeks Surgery or radiation therapy within the past 6 weeks Serious medical co-morbidities, which would otherwise contraindicate surgery, as determined by the investigator Currently pregnant or nursing Psychotic diseases, epilepsy, or any history of such diseases Current abuse of alcohol (> 10 drinks weekly) and/or regular exposure to other substances of abuse, currently an active smoker Chronic inflammatory articular diseases such as rheumatoid arthritis Enrolled in any other clinical trials within the past 4 weeks Administered immunosuppressants such as Cyclosporin A or azathioprine within the past 6 weeks Ligament instability > Grade II Uncorrected significant lower extremity malalignment (i.e. > 5 degrees) (sub-) Total meniscectomy (<5mm rim remaining) Corticosteroid or viscosupplementation injection to the affected knee in the past 3 months Principal investigator considers inappropriate for the clinical trial due to any reasons other than those listed above
Number of Patients	12 patients in total; 6 patients with defect sizes of 2-5 cm ² followed by 6 patients with defect sizes > 5 cm ²
Number of Study Centers	Two
Concomitant Treatment	Patients should discuss any medications and therapies they are currently taking with the study doctor. Patients in this trial must not take the following drugs: glucosamine, dietary supplements used as alternative medicine to treat osteoarthritis such as chondroitin sulfate and hyaluronan, systemically administered corticosteroids (Hydrocortisone, Prednisone, Prednisolone, Methylprednisolone, Triamcinolone, Dexamethasone, Paramethasone, Betamethasone, Aldosterone, Fludrocortisone) and immunosuppressants (Prednisone, Vincristine, Azathioprine, γ – globulin, Cyclophosphamide, Chlorambucil, 6-mercaptopurine, Cyclophosphamide + factor XIII, Rh(D) immune globulin, ALG, Actinomycin-D, OKT3, Methotrexate)

page 4 of 137

CONFIDENTIAL: These all contents herein are the sole property of MEDIPOST Co., Ltd. Any reproduction or distribution of this document without the written consent of MEDIPOST Co., Ltd is prohibited. Copyright © 2017 MEDIPOST Co., Ltd.

page 5 of 137

CONFIDENTIAL: These all contents herein are the sole property of MEDIPOST Co., Ltd. Any reproduction or distribution of this document without the written consent of MEDIPOST Co., Ltd is prohibited. Copyright © 2017 MEDIPOST Co., Ltd.

Clinical Trial Material (CTM)	CARTISTEM [®] (human allogeneic-unrelated umbilical cord blood-derived mesenchymal stem cells, hUCB-MSC, and sodium hyaluronate) CARTISTEM [®] consists of approximately 7.5 x 10 ⁶ hUCB-MSC suspended in 1.5 mL medium in one vial, and 60 mg sodium hyaluronate provided as a lyophilized sponge form in a separate vial. The two vials are mixed at the surgical site. Upon admixture of the two vials, the combination forms a viscous gel, which is implanted into the articular cartilage defect.
Clinical Trial Material Dosage and Administration	CARTISTEM [®] will be administered into the articular cartilage defect by open surgery at a dose of 0.5 mL/cm ² based upon size of the defect. The CARTISTEM [®] dosage has been selected based on the results derived from nonclinical studies and prior human experience (see Investigator's Brochure for further information)
Surgical Technique	Before application of CARTISTEM [®] , unstable chondral fragments are debrided using a curet and stable shoulders of healthy surrounding cartilage are created. After adequate removal of the debris, multiple holes are created across the entire articular cartilage defect with a 2~3 mm drill bit spacing the holes approximately 3~5 mm apart. CARTISTEM [®] is applied onto the drilled holes first, and then throughout the entire cartilage defect.
Post-operative rehabilitation	Patients will be started on a continuous passive motion (CPM) device on post-operative day 1 with a range of motion of 0-30 degrees initially. This will be increased by 10 degrees per day as tolerated to a maximum of 0-90 degrees. Patients will undergo CPM treatment for 6 hours per day over 6 weeks. The patient will remain touch-down weight-bearing (TDWB) for 6 weeks, and then advance to full-weight bearing during the next 6 weeks (up to week 12). The patient will refrain from high-impact activities, such as running, during the subsequent 8 to 12 weeks (week $20 - 24$).
Reference Therapy	The study does not include a reference compound.
Approximate Duration of Patient Participation	Each patient will undergo a 6-week screening period for eligibility and a 12- month follow-up observation period for both the primary (safety) and secondary (efficacy) evaluations following administration of CARTISTEM [®] . Also each patient will undergo a 24-month follow-up visit for a long term patient assessment.

page 6 of 137

CONFIDENTIAL: These all contents herein are the sole property of MEDIPOST Co., Ltd. Any reproduction or distribution of this document without the written consent of MEDIPOST Co., Ltd is prohibited. Copyright © 2017 MEDIPOST Co., Ltd.

Approximate Duration of Study	The estimated duration of the study for the primary evaluation is approximately 12 months, with an additional 12 month extension for the long-term patient assessment phase.
Safety Evaluation	General General safety will be evaluated via the following assessments: AEs, routine clinical laboratory tests (hematology, clinical chemistry, and urinalysis), thrombin generation (PT and aPTT), immunogenicity tests (T cell subset), vital signs, physical exams, ECGs, and MRI for tumorigenicity.
	 Adverse Events To assess the safety of CARTISTEM[®], the course and degree of swelling, tenderness, range of motion and pain will be determined. DLT is defined as toxicity or adverse event of Grade 3 or higher [80 points or higher for pain] in two or more events at the surgery site among swelling, tenderness, range of motion, and pain, in any one visit. DLT is also defined as adverse drug reaction of Grade 3 or higher in the Common Toxicity Criteria Adverse Events (CTCAE), Version 4.0, with the exception of the following events and that they are unresolved for 7 consecutive days, despite medical interventions: Abnormal results in lab test (Acidosis, Hyponatremia, Hyperbilirubinemia, etc.) Fatigue, defined as not relieved by rest; limiting self-care ADL Pain, defined as severe pain in various parts of the head, limiting self-care ADL Fever, defined as >40.0 degrees C (> 104.0 degrees F) for > 24 hours
Efficacy Evaluation	Primary efficacy outcome parameters will be the postoperative changes in subjective knee function as assessed by IKDC (International Knee Documentation Committee) score at 12 months. For secondary efficacy outcome parameters, patients will answer questionnaires for pain (visual analogue scale, VAS), knee specific outcome instruments (Lysholm knee scoring, and KOOS [Knee injury and Osteoarthritis Outcome Score]). Structural information will be gathered using high-resolution (1.5 or 3 Tesla) magnetic resonance imaging (MRI).

page 7 of 137

CONFIDENTIAL: These all contents herein are the sole property of MEDIPOST Co., Ltd. Any reproduction or distribution of this document without the written consent of MEDIPOST Co., Ltd is prohibited. Copyright © 2017 MEDIPOST Co., Ltd.

Statistical Methods	General: all safety and efficacy endpoints will be presented for each dose cohort as well as for all patients combined. For safety evaluation, statistical homogeneity between dose groups will be performed. For efficacy evaluation, statistical comparison (difference) between dose groups will be performed.
	1) Safety Safety will be demonstrated with 95% confidence intervals. Adverse events, adverse drug reactions, serious adverse events, and drop-out patients due to AE will be presented with frequency and percentage. Homogeneity between dose groups will be analyzed using person's chi-square test or Fisher's exact test. Descriptive statistics including means, medians, SD (standard deviation), minimum and maximum will be used to demonstrate the other safety endpoints.
	2) Efficacy Symptom improvement from the outcome instruments will be demonstrated with means and standard deviations. Efficacy results will also be analyzed for statistical significance using change from baseline at each efficacy endpoint. Statistical difference of continuous variables and categorical variables between dose groups will be compared using t-test and Fisher's exact test, respectively.
Rationale for Study Population and Number of Patients	CARTISTEM [®] is administered to the defective joint cartilage region by open surgery. Due to ethical considerations, it is not possible to conduct this type of procedure in a healthy subject. Therefore, no studies in healthy subjects will be performed.
	Factors such as number of subjects to acquire statistical data of the effectiveness are not considered as critical in this phase I/IIa study. A small number of subjects generally participate in this stage of clinical study. Accordingly, Dosage A is set based on dose limit of toxicity from non-clinical study and then Dosage B will be administered.

page 8 of 137

CONFIDENTIAL: These all contents herein are the sole property of MEDIPOST Co., Ltd. Any reproduction or distribution of this document without the written consent of MEDIPOST Co., Ltd is prohibited. Copyright © 2017 MEDIPOST Co., Ltd.

Abbreviations

AE	Adverse Event, Adverse Experience
ADR	Adverse Drug Reaction
ALP	Alkaline Phosphatase
ALT(sGPT)	Alanine aminotransferase (serum Glutamic Pyruvic Transaminase)
AST(sGOT)	Aspartate aminotransferase (serum Glutamic Oxaloacetic Transaminase)
BUN	Blood Urea Nitrogen
СК	Creatine Kinase
CRP	C-Reactive Protein
CTC	Common Toxicity Criteria
DLT	Dose Limiting Toxicity
ESR	Erythrocyte Sedimentation Rate
HCG	Human Chronic Gonadotropin
Hb	Hemoglobin Concentration
Hct	Hematocrit
ICRS	International Cartilage Repair Society
IKDC	International Knee Documentation Committee
IND	Investigational New Drug
KOOS Score	Knee injury and Osteoarthritis Outcome Score
LDH	Lactate dehydrogenase
МСН	Mean Corpuscular Hemoglobin
MCHC	Mean Corpuscular Hemoglobin Concentration
MCV	Mean Corpuscular Volume
MLR	Mixed Lymphocyte Reaction
MTD	Maximal Tolerated Dose
NCI	National Cancer Institute
РТ	Prothrombin Time
aPTT	Activated Partial Thromboplastin Time
RBC	Red Blood Cell
ROM	Range of Motion
VAS	Visual Analogue Scale
WBC	White Blood Cell

CARTISTEM®

page 9 of 137

CONFIDENTIAL: These all contents herein are the sole property of MEDIPOST Co., Ltd. Any reproduction or distribution of this document without the written consent of MEDIPOST Co., Ltd is prohibited. Copyright © 2017 MEDIPOST Co., Ltd.

Table of Contents

1	Title and Development of Phase	

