10.3.2 Analysis of Efficacy Endpoints

The descriptive statistics of the categorical variables will be presented with percentage and frequency and that of the continuous variables such as mean, median, standard deviation, and interquartile range. The primary efficacy endpoint will be analyzed using the t-test. As for the secondary efficacy endpoints, differences of the continuous variables and the categorical variables between the two groups will be analyzed using the t-test and Fisher's exact test, respectively.

CONFIDENTIAL: These all contents herein are the sole property of MEDIPOST Co., Ltd. Any reproduction or distribution of this document without the written consent of MEDIPOST Co., Ltd is prohibited. Copyright © 2017 MEDIPOST Co., Ltd

11 Rehabilitation Protocol

All patients must participate in the following standardized rehabilitation program after receiving treatment. Rehabilitation program will vary according to the defect location of each subject.

Stage 1- Proliferative Phase (Week 1 to 6)

Femoral Condyle Defect

	PRIMARY GOALS
	DO NOT OVERLOAD GRAFT
	INCREASE TIBIOFEMORAL AND PATELLOFEMORAL MOBILITY
	RESTORE QUADRICEPS CONTROL
BRACE	• Knee immobilizer with ambulation, until good quads control/SLR (approximately Week 3 to 6)
GAIT	Heel-toe TDWB with crutches
ROM	• Full AROM and gentle AAROM.
	 CPM ≥ 6 to 8 hours daily for 6 weeks. Start at 0-40 degrees, progress range as tolerated.
	• Goal: minimum 90 degrees flexion for the first 2 weeks, 110 degrees for the next 4 weeks (the 6 week time point of post-op)
THEREX	• Quad sets, SLR in knee immobilizer as needed, leg curl/heel slides, hip abduction
	 Stationary bicycle with no resistance once 90 degrees knee flexion obtained (~ 4 weeks).
	 90 degree leg dangle hourly to improve ROM
THERAPY	 Gentle multi-directional patella mobilization starts immediately after surgery. Cryotherapy and compression stockings/TEDS for swelling and pain control. E-stim for VMO/quadriceps muscle re-education/biofeedback encouraged
	early after surgery if needed.
	 Gentle massage/deep friction to hamstring insertions, suprapatellar quadriceps, medial/lateral gutters, and infrapatellar fat pad region at 2-3 weeks post-op.
	 Pool therapy recommended 2-3 weeks post-op to enhance motion.
	• Foot merapy recommended 2-5 weeks post-op to emiance motion.

page 44 of 137

Femoral Condyle Defect

PRIMARY GOALS DO NOT OVERLOAD GRAFT INCREASE TIBIOFEMORAL AND PATELLOFEMORAL MOBILITY RESTORE QUADRICEPS CONTROL

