BRACE	• Knee brace may be discontinued once independent SLR achieved
GAIT	• Week 7 & 8: 50% weight-bearing, week 9+: full weight-bearing
ROM	 Full AROM and gentle PROM exercises Progress towards full ROM until the 12 week time point.
THEREX	 Low weight (max 10-20lbs.) open-chain leg extension and curl Stationary bicycle with gradual increased tension per level of comfort Continue quad sets, SLR in brace, leg curl and heel slides
	 Strengthen quadriceps, hamstrings, and hip abductors/extensors using ankle weights and/or elastic band resistance through full ROM as tolerated Gentle closed-chain terminal knee extension 0 to 40 degrees (TKE) permitted starting from the nine or ten week time point as tolerated per weight bearing restriction
THERAPY	 Gentle multi-directional patella mobilization Cryotherapy and compression stockings/TEDS for swelling and pain control E-stim for VMO/quadriceps muscle re-education/biofeedback encouraged Gentle massage/deep friction to hamstring insertions, suprapatellar quadriceps, medial/lateral gutters, and infrapatellar fat pad region Pool therapy recommended to enhance motion

page 45 of 137

CONFIDENTIAL: These all contents herein are the sole property of MEDIPOST Co., Ltd. Any reproduction or distribution of this document without the written consent of MEDIPOST Co., Ltd is prohibited. Copyright © 2017 MEDIPOST Co., Lt

-- or for trochlear defects --

Stage 1- Proliferative Phase (Week 0 to 6)

Trochlear Defect

	PRIMARY GOALS DO NOT OVERLOAD GRAFT INCREASE TIBIOFEMORAL AND PATELLOFEMORAL MOBILITY RESTORE QUADRICEPS CONTROL
BRACE	 Bledsoe Hinge knee brace for ambulation (locked) and at night Out of brace for CPM. No brace, but towel/pillow behind heel when lying down
PRECAUTIONS	• Full weightbearing in full extension (locked brace)
ROM	 Gentle AROM flexion as tolerated 3x/day. Only PROM extension allowed. CPM ≥ 6 to 8 hours daily. Starting from 0 to 40 degrees, progress range as tolerated after the first 2 weeks. Minimum 90 degrees flexion for the first 2 weeks, 110 degrees for the next 4 weeks
THEREX	 Quad sets, SLR with brace locked, leg curl/heel slides, hip abduction Stationary bicycle with no resistance once 90 degrees knee flexion obtained (> 4wks). 90 Degree Leg dangle hourly to improve ROM

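### The synopsis and Section 11 contradict each other on weight-bearing after trochlear repair and on CPM start and progression, within the 12-week DLT window

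*Combined protocol and SAP*

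**What the plan says.** The synopsis, under Post-operative rehabilitation, gives a single regimen with no exception by defect location. On loading: "The patient will remain touch-down weight-bearing (TDWB) for 6 weeks", "and then advance to full-weight bearing during the next 6 weeks (up to week 12". CPM begins on post-operative day 1 "with a range of motion of 0-30 degrees initially". It continues: "This will be increased by 10 degrees per day as tolerated to a maximum of 0-90 degrees". On dose: "Patients will undergo CPM treatment for 6 hours per day over 6 weeks".

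Section 11 requires all patients to follow its standardized program and says that the program depends on where the defect lies. It then gives two versions.

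- **Femoral condyle.** Touch-down weight-bearing with crutches in weeks 1-6, then "Week 7 & 8: 50% weight-bearing, week 9+: full weight-bearing". For CPM: "Start at 0-40 degrees, progress range as tolerated", at least 6 to 8 hours daily for 6 weeks.
- **Trochlea, weeks 0-6.** "Full weightbearing in full extension (locked brace". CPM also starts at 0-40 degrees for at least 6 to 8 hours daily, with range progressed as tolerated once two weeks have passed.

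Both versions also list flexion figures of at least 90 degrees for the first 2 weeks and 110 degrees for the next 4. Section 5 repeats that CPM starts on day 1 but gives no range and no loading rule. No section says whether the synopsis or Section 11 takes precedence.

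**The concern.** A trochlear patient cannot be both touch-down and fully weight-bearing in the same weeks, and a first CPM session cannot start at both 0-30 and 0-40 degrees. A site can therefore comply with one part of the protocol only by departing from another.

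Safety is the primary objective, and this is where it matters most. Under the synopsis and Section 6.6, one route to a DLT is Grade 3 or higher (80 points or higher for pain) in two or more of swelling, tenderness, range of motion and pain at the surgery site at any one visit. How the knee is loaded and moved could plausibly influence these signs, and both Section 11 versions name avoiding graft overload as their first goal. Under Section 6.5, one or two DLTs among the Dosage A patients add 3 patients, and three halt the study. With 6 patients in the cohort, a single local event changes the course of the trial. If patients have been rehabilitated under different texts, that event is harder to attribute to the product.

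**Working it through.** The plan states no figure to reproduce here, so the check is a comparison of the texts with some short arithmetic.

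| Element | Synopsis (all patients) | Section 11, condyle | Section 11, trochlea | Compatible? |
|---|---|---|---|---|
| Weight-bearing to week 6 | Touch-down | Touch-down | Full, locked brace | Condyle yes; trochlea **no** |
| Weight-bearing after week 6 | Advance to full, up to week 12 | 50% in weeks 7-8, full from week 9 | Full as tolerated | Condyle yes, inside the window |
| CPM start | 0-30 degrees | 0-40 degrees | 0-40 degrees | **No**, either location |
| CPM progression | +10 degrees/day as tolerated | As tolerated | As tolerated after 2 weeks | **No** common rule |
| CPM cap | 0-90 degrees | None stated | None stated | **No** common rule |
| CPM hours per day | 6 | At least 6 to 8 | At least 6 to 8 | Overlap at 6 |

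**CPM timing under the synopsis.** With 30 degrees on post-operative day 1 and 10 more each day, the range on day d is 30 + 10(d - 1). Setting this equal to 90 gives d = 7. The trochlear text, read literally, still has 0-40 on day 7, a gap of 90 - 40 = 50 degrees if every synopsis step is tolerated. One caution: the same trochlear row asks for at least 90 degrees of flexion in the first 2 weeks, so how strictly the two-week hold is meant is itself unclear.

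**CPM hours.** Over 6 weeks (42 days) the synopsis gives 6 x 42 = 252 hours. Section 11 gives 252 hours at 6 a day and 8 x 42 = 336 at 8 a day. Six hours satisfies the lower end, so this is loose wording and not a contradiction.

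**Overlap with DLT assessment.** Dosage A is judged on DLT over 12 weeks. The Section 8.2 flow chart has post-treatment visits at weeks 2, 4, 8 and 12, and Section 8.4.3 has toxicity evaluated at each follow-up visit. Weeks 2 and 4, two of the four visits, fall inside the weeks in which the texts disagree on trochlear loading and on CPM. Week 8 follows soon after.

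**IKDC, as illustration only.** The documents give no SD and no rehabilitation effect, so both are assumed. If 3 more patients in one 6-patient cohort than in the other follow a given text, the bias in the A-versus-B mean difference is (3/6) x effect. For effects of 0.2, 0.5 and 0.8 SD this is 0.10, 0.25 and 0.40 SD. A two-sided 5% t-test of 6 against 6 would then reject, with no dose effect, in 5.3%, 6.8% and 9.6% of trials. The 95% confidence interval for that comparison has a half-width of 2.228 x sqrt(2/6) = 1.29 SD, so sampling error is far larger than any of these biases.

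**The case against.** The strongest reply is that Section 11 is plainly the operative text and the synopsis only a summary; that variation by defect location is intended; and that Section 8.3 already requires concurrent therapies, with physiotherapy as its example, to be recorded on the CRF by type and duration. Much of this stands. Intended variation by location is not a defect, and no new data-collection system is needed. But no clause gives Section 11 precedence, the synopsis allows no exception by location, and Section 8.3 does not mention CPM range or weight-bearing stage.

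A reader might also draw stronger conclusions that the documents do not support:

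- **That weight-bearing conflicts for condylar defects too.** It does not. Both texts have touch-down loading to week 6, and week 12 in the synopsis is an outer limit within which full loading from week 9 falls.
- **That the 0-90 cap conflicts with the 110-degree figure.** The first is a CPM setting. The second is a flexion figure, labelled a goal in the condylar table, in a row that also covers active motion. The two can coexist.
- **That CPM duration conflicts.** The 6-week course is the same where stated, and the daily hours overlap.
- **That the inconsistency confounds the 12-month IKDC result.** No effect of these differences on IKDC is given, efficacy is exploratory, and either text allows full weight-bearing by week 12.
- **That two centers will follow different pages.** The synopsis says two centers and Section 5 says single-center; divergent practice is possible under either but is not shown.

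**Conclusion.** The contradiction is real and limited to two matters: weight-bearing for trochlear defects in weeks 0-6, and the start, progression and cap of CPM for both locations. It is an internal inconsistency in a mandatory co-intervention, and it falls in the period when local signs can decide whether Dosage B opens. Its consequence is weaker attribution of a local DLT to the product. That rests on the assumption that patients could in practice be managed under different texts, which the protocol leaves open. The size of any effect on DLT cannot be derived from the documents. Any effect on 12-month IKDC remains a possibility, and under the assumed range above it is modest beside the imprecision of a 6-versus-6 comparison. This review takes no position on which loading or CPM rule is right.

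**What to change.** The sponsor and surgical investigators must reconcile the synopsis and Section 11 into one regimen per defect location. The synopsis should then refer to that text instead of giving its own regimen.

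Make the existing Section 8.3 CRF record specific: defect location, CPM range and daily hours, and weight-bearing stage. Each DLT can then be read against the rehabilitation actually received.

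The cost is amended wording and a few more specific entries in a record the protocol already requires. No visit, procedure or patient is added.
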